### 2.4 Correlative Studies Background

Correlative studies may be performed in the Immune Oncology and DNA Repair Centers here at DFCI and Ventana Medical Systems. Depending on funding availability these may include: i) determination of CD3+, CD8+ TILs, CD8+/CD4+FOXP3+ TIL ratio, CD137+CD8+ TILs, CD137+CD8+/CD4+FOXP3+ TIL ratio, peritumoral lymphocytes and correlation with response; ii) expression of immune checkpoints including TIM-3, LAG-3, CTLA-4, PD-L2, PD-L1, PD-1, IDO and correlation with response; iii) targeted next generation sequencing (Oncopanel) to determine specific genetic alterations and correlate with response

The identification of predictive correlates to response to treatment with checkpoint blockade has proven a critical, but elusive goal, with numerous proposed approaches across different tumor types, but none that has thus far gained widespread clinical acceptance [24, 25]. Several efforts have focused on the identification of PD-L1 expression via immunohistochemistry (IHC) on the

surface of tumor, or infiltrating immune cells. Some studies have suggested a significant correlation between tumoral PD-L1 expression and response in nonsmall cell lung cancer [26], although others utilizing a similar approach have failed to identify a significant correlation [27, 28]. Notable challenges in this strategy include the lack of standardization among IHC assays, the use of differential thresholds for assay positivity and a lack of consensus regarding the importance of explicitly accounting for PD-L1 expression on infiltrating immune cells. Complicating the development of these approaches are concerns that inadequate negative predictive value and full understanding of the underlying immune dynamics between the host and tumor may result in the exclusion of patients who may benefit from treatment.

For this trial we may characterize PD-L1 and PD-L2 expression on tumor cells and infiltrating immune cells in baseline formalin fixed paraffin embedded (FFPE) blocks of cancer tissue (which are required for eligibility) in conjunction with the Dana Farber Cancer Institute Center for Immunooncology. We may also characterize CD3+ T-cells, CD8+ T-cells and CD4+ T-cells as well as other immune cell markers and checkpoints in baseline FFPE blocks of cancer tissue.

Although less advanced in clinical development and practice, characterization of ex vivo surface markers on tumor cells, T-cells and other immune cells via multiparametric analysis (e.g. via flow cytometry or mass cytometry) has significant potential to reveal predictive biomarkers given the ability to measure multifarious combinations and to identify combinatorial patterns of expression among diverse cell populations. Using multiparametric assays developed in conjunction with the Dana Farber Cancer Institute Center for Immunooncology, we may determine the relative frequencies of T-cell subsets and evaluate the expression of immune checkpoints PD-1, PD-L1, PD-L2 and other immunologically active markers including TIM-3, LAG-3, CTLA-4, and IDO.

Genomic predictive correlates for response to checkpoint blockade have taken several forms. First, and serving as a critical line of evidence supporting this trial, numerous studies have suggested a correlation between mutational and neoepitope burden and response to checkpoint blockade [14, 29, 30]. Furthermore, as noted above, identification of microsatellite instability resulting from defects in the mismatch repair pathway and specifically within MLH1, MSH2, MSH6 and PMS2 have been suggested to portend a significantly improved response to checkpoint blockade [14]. This trial is limited to MSS tumors, therefore additional genomic alterations that correlate with response to the combination may be sought by characterizing genomic changes in FFPE tissue specimen. These include specific DNA gene repair mutations, neoantigens, and single nucleotide polymorphisims (SNPs) in immunologically relevant genes.

### PARTICIPANT SELECTION

Remote consenting procedures may be implemented in the FR $\alpha$  pre-screening process for this trial as allowed per institutional policy.

3.1 Eligibility Criteria

3.1.1 Participants must have advanced or recurrent **serous endometrial cancer**. Patients with mixed histologies/tumors are eligible if the serous component is the dominant histological subtype. In addition, the tumors must be:

1) microsatellite stable (MSS) as documented by either intact immunohistochemical (IHC) nuclear expression of the mismatch repair genes MSH2, MSH6, MLH1 and PMS2; or microsatelitte stable by polymerase chain reaction (PCR), next generation sequencing, or other CLIA-approved method;

### AND

2) **FRa positive** by central immunohistochemistry (IHC, Section 9.1). If archival tissue does not meet FRa criteria, a fresh biopsy tumor sample may be submitted and used to meet this criterium. If a fresh tumor biopsy cannot be done safely the patient will not be allowed to enroll on this study.

- 3.1.2 Participants must have measurable disease as defined by RECIST 1.1. Lesions situated in a previously irradiated area are considered measurable if progression has been demonstrated in such lesions.
- 3.1.3 Prior therapy: Patients must have had one, but no more than four lines of chemotherapy for endometrial carcinoma.
  - Prior hormonal therapy is allowed (no washout period is required after hormonal therapy) and does not count as a prior line of therapy. Hormonal therapy in combination with CDK4/6 inhibitors or mTOR or other PI3K-pathway inhibitors is allowed and does not count as a line of prior therapy.
  - Prior IO therapy targeted to the PD-1/PD-L1 pathway is allowed in up to 19 patients of the total cohort.
  - Patients must NOT have received prior therapy with any folate receptor ortholog agents.
- 3.1.4 Age 18 or greater years. Because insufficient dosing or adverse event data are currently available on the use of mirvetuximab soravtansine and pembrolizumab in participants <18 years of age, children are excluded. Endometrial cancer is rare in the pediatric population.

- 3.1.5 ECOG performance status 0 or 1
- 3.1.6 Availability of archival tissue for research purposes in the form of a formalin-fixed paraffin embedded (FFPE) block or 5 unstained slides (Section 9). Participants without available archival tissue may be eligible for enrollment after discussion with the Principal Investigator.
- 3.1.7 Participants must have normal organ and marrow function as defined below:

_	leukocytes	≥3,000/mcL
_	absolute neutrophil count	>1,500/mcL

NCI Protocol #: N/A DF/HCC Protocol #: 18-602 Protocol Version Date: December 11, 2023

		······ · · · · · · · · · · · · · · · ·
_	platelets	≥100,000/mcL
_	hemoglobin	$\geq$ 9.0 g/dL
_	total bilirubin	$\leq$ 1.5 x institutional upper limit of normal
_	AST(SGOT)/ALT(SGPT)	$\leq 2.5 \times$ institutional upper limit of normal
_	creatinine	$\leq$ institutional upper limit of normal
		OR
_	creatinine clearance	$\geq$ 40 mL/min/1.73 m  for participants with creatinine
		levels above institutional normal.

- 3.1.8 Time from prior therapy:
  - a. Systemic anti-neoplastic therapy: 5 half-lives or 4 weeks, whichever is shorter. Hormonal therapy is not considered anti-neoplastic therapy.
  - b. Radiotherapy: wide-field radiotherapy (e.g. > 30% of marrow-bearing bones) completed at least 4 weeks, or focal radiation completed at least 2 weeks, prior to starting study treatment
- 3.1.9 The effects of agents used in this study on the developing human fetus are unknown. For this reason, women of child-bearing potential must agree to use adequate contraception (hormonal or barrier method of birth control; abstinence) prior to study entry, during study treatment, and for at least twelve weeks after the last dose of study treatment. Should a woman become pregnant or suspect she is pregnant while she is participating in this study, she should inform her treating physician immediately.
- 3.1.10 Women of child-bearing potential must have a negative serum pregnancy test within 3 days prior to the first dose of study treatment.
- 3.1.11 Ability to understand and the willingness to sign a written informed consent document.

### 3.2 Exclusion Criteria

- 3.2.1 Participants who have had chemotherapy within 5 half-lives or 4 weeks (whichever is shorter) or radiotherapy within 2 weeks prior to entering the study. Patients completing wide-field radiotherapy (e.g. >30% of marrow-bearing bones) must not have had treatment within 4 weeks prior to entering study. Participants must have recovered from all AEs due to previous therapy to Grade  $1 \le$  or baseline, except alopecia. Participants with endocrine-related AEs who are adequately treated with hormone replacement are eligible.
- 3.2.2 Participants who are receiving any other investigational agents.
- 3.2.3 Participants with prior exposure to IO agents targeting the PD-1/PD-L1 pathway who discontinued therapy due to treatment-related toxicity deemed to be specifically related to IO therapy.
- 3.2.4 Required use of folate-containing supplements (e.g. folate deficiency).

- 3.2.5 Known active CNS metastases and/or carcinomatous meningitis. Participants with previously treated brain metastases may participate provided they are radiologically stable, i.e. without evidence of progression for at least 4 weeks by repeat imaging (note that the repeat imaging should be performed during study screening), clinically stable and without requirement of steroid treatment for at least 14 days prior to first dose of study treatment.
- 3.2.6 History of allergic reactions attributed to compounds of similar chemical or biologic composition to monoclonal antibodies (including antibody drug-conjugates or checkpoint inhibitors).
- 3.2.7 Uncontrolled intercurrent illness including, but not limited to, any of the following within 6 months of first study treatment: symptomatic congestive heart failure, unstable angina pectoris, uncontrolled hypertension (≥ Grade 3), hypertensive crisis or hypertensive encephalopathy, uncontrolled cardiac arrhythmias, thrombotic or ischemic stroke, clinically-significant vascular disease (e.g. aortic aneurysm, or dissecting aneurysm), severe aortic stenosis, clinically significant peripheral vascular disease, or ≥ Grade 3 cardiac toxicity following prior chemotherapy, cardiac arrhythmia, or psychiatric illness/social situations that would limit compliance with study requirements.
- 3.2.8 Active or chronic corneal disorder, including but not limited to the following: Sjogren's syndrome, Fuchs corneal dystrophy (requiring treatment), history of corneal transplantation, active herpetic keratitis, and also active ocular conditions requiring on-going treatment/monitoring such as wet age-related macular degeneration requiring intravitreal injections, active diabetic retinopathy with macular edema, presence of papilledema, and acquired monocular vision.
- 3.2.9 Serious clinically-relevant active infection, including known HIV infection, varicellazoster virus, cytomegalovirus infection, has a known history of Hepatitis B (defined as Hepatitis B surface antigen [HbsAg] reactive) or known active Hepatitis C virus (defined as HCV RNA is detected) or any other known concurrent infectious disease requiring IV antibiotics with within 2 weeks of study enrollment are ineligible because of the potential for immune side effects.
- 3.2.10 Has received a live vaccine or live-attenuated vaccine within 30 days prior to the first dose of study drug. Administration of killed vaccines is allowed.
- 3.2.11 Current or prior use of immunosuppressive medication within 7 days prior to enrollment with the following exceptions to this exclusion criterion:
  - a. Intranasal, inhaled, topical steroids, or local steroid injections (eg, intra-articular injection);
  - b. Systemic corticosteroids at physiologic doses not to exceed 10 mg/day of prednisone or equivalent;
  - c. Steroids as premedication for hypersensitivity reactions (eg, CT scan premedication).

- 3.2.12 Active autoimmune disease that might deteriorate when receiving an immunostimulatory agent. Patients with diabetes type I, vitiligo, psoriasis, hypo-or hyperthyroid disease not requiring immunosuppressive treatment are eligible.
- 3.2.13 Has a history of (non-infectious) pneumonitis/interstitial lung disease that required steroids or has current pneumonitis/interstitial lung disease.
- 3.2.14 Pregnant or nursing women are excluded from this study because effects of agents used in this study on infants or the developing human fetus are unknown
- 3.2.15 Presence of other malignancies unless they are considered cured by patient's oncologist.

### 3.3 Inclusion of Women and Minorities

Women of all races and ethnic groups are eligible for this trial. This disease does not affect men.

### **REGISTRATION PROCEDURES**

### 4.1 General Guidelines for DF/HCC Institutions

Institutions will register eligible participants in the Clinical Trials Management System (CTMS) OnCore. Registrations must occur prior to the initiation of any protocol-specific therapy or intervention. Any participant not registered to the protocol before protocol-specific therapy or intervention begins will be considered ineligible and registration will be denied.

An investigator will confirm eligibility criteria and a member of the study team will complete the protocol-specific eligibility checklist.

Following registration, participants may begin protocol-specific therapy and/or intervention. Issues that would cause treatment delays should be discussed with the Overall Principal Investigator (PI). If the subject does not receive protocol therapy following registration, the subject must be taken off-study in the CTMS (OnCore) with an appropriate date and reason entered.

## 4.2 **Registration Process for DF/HCC Institutions**

Applicable DF/HCC policy (REGIST-101) must be followed.

## 4.3 General Guidelines for Other Investigative Sites

Eligible participants will be entered on study centrally at the Dana-Farber Gynecologic Oncology Coordinating Center by the Project Manager. All sites should contact the Project Manager ([name]; [name]\[contact]) when a potential participant is identified to confirm enrollment availability.

Following registration, participants should begin protocol therapy within 5 days. Issues that would cause treatment delays should be discussed with the Overall PI. If the subject does not receive protocol therapy following registration, the subject must be taken off study in the CTMS (OnCore) with an appropriate date and reason entered.

### 4.4 Registration Process for Other Investigative Sites

To register a participant, the following documents should be completed by the participating non-DF/HCC site and e-mailed ([name]\[contact]) to the Project Manager:

- Copy of required laboratory tests: complete blood count with differential and serum chemistries (including liver function tests)
- Screening clinic note (including documentation of oncologic history, past medical history, concomitant medications, performance status, and vitals)
- Pathology report (with documentation of MSS status)
- CT scan (with documentation of measurable disease per RECIST 1.1)
- Documentation of FRα positivity
- Clinic note from pulmonary function test
- Clinic note from eye exam
- Documentation of consent process
- Signed informed consent form
- HIPAA authorization form (if separate from the informed consent document)
- Eligibility Checklist

The participating site will then e-mail ([name]\[contact]) the Project Manager to verify eligibility. The Project Manager will follow DF/HCC policy (REGIST-101) and register the participant on the protocol. The Project Manager will e-mail the participant study number, and if applicable the dose treatment level, to the participating site.

#### TREATMENT PLAN

#### 5.1 Treatment Regimen

Treatment will be administered on an outpatient basis.

Following premedications, mirvetuximab soravtansine will be administered at 6 mg/kg by Adjusted Ideal Body Weight (AIBW) intravenously on Day 1 of a 21-day cycle. Then, pembrolizumab will be administered intravenously over 30 minutes at 200 mg flat dose on Day 1 of 21-day cycle (one cycle =21 days), after all procedures and assessments have been completed. Study medications may be administered up to 3 days before or after the scheduled day of administration of each cycle due to administrative reasons.

The duration of treatment with the combination will be until progression or adverse event up to 35 cycles. Beyond 35 cycles, mirvetuximab soravtansine will be continued until progression or adverse event.

Agent	Dose	Route	Schedule	Cycle Length
Mirvetuximab soravtansine	6 mg/kg	IV before	Day 1 each	
(IMGN853)*	(AIBW)	Pembrolizumab	cycle	21 days
		+/- 10 min**		$\frac{21 \text{ uays}}{(2 \text{ weaks})}$
Pembrolizumab	200 mg	IV over 30	Day 1 each	(5 weeks)
		minutes -5/+10	cycle	
		min		
*Note: Mirvetuximab soravtansine is incompatible with 0.9% sodium chloride (saline)				
** Infusion rate will vary based on patient tolerability as described in Section 5.3.1				

Reported adverse events and potential risks are described in Section 7. Appropriate dose modifications are described in Section 6. No investigational or commercial agents or therapies other than those described below may be administered with the intent to treat the participant's malignancy.

### 5.2 **Pre-Treatment Criteria**

- 5.2.1 Cycle 1, Day 1 (or within 7 days prior to Cycle 1, Day 1)
  - Absolute neutrophil count  $\geq$ 1,500/mcL
  - Platelets  $\geq 100,000/mcL$
  - Hemoglobin  $\geq 9g/dL$
  - Total bilirubin  $\leq 1.5$  x institutional upper limit of normal
  - AST (SGOT) / ALT (SGPT)  $\leq 2.5$  x institutional upper limit of normal
  - Creatinine  $\leq$  institutional upper limit of normal or creatinine clearance  $\geq$  40 mL/min/1.73 m2 for subjects with creatinine levels above institutional normal
  - All toxicities of previous therapy (aside from alopecia) must have resolved to  $\leq$  grade 1
  - ECOG performance of 0 or 1
  - No evidence of life-threatening medical problems

## 5.2.2 Subsequent Cycles

- Absolute neutrophil count  $\geq$ 1,000/mcL
- Platelets  $\geq$ 75,000/mcL
- AST (SGOT) / ALT (SGPT)  $\leq 2.5$  x institutional upper limit of normal
- Creatinine ≤ institutional upper limit of normal or creatinine clearance >= 40 mL/min/1.73 m2 for subjects with creatinine levels above institutional normal
- All toxicities pf previous cycles must have resolved to  $\leq$  grade 2
- ECOG performance of 0 to 2
- No evidence of life-threatening medical problems

### 5.3 Agent Administration

## 5.3.1 Mirvetuximab Soravtansine (IMGN853)

Dosing

Mirvetuximab soravtansine 6 mg/kg by Adjusted Ideal Body Weight (AIBW) IV on Day 1 of each 21-day cycle. Dosing by AIBW as follows:

### Adjusted Ideal Body Weight (AIBW)

 $IBW^1 + 0.4$  (Actual weight –  $IBW^1$ )

Where:

# Ideal Body Weight (IBW)

 $IBW^{1}$  (male) =  $0.9H^{1}-88$  $IBW^{1}$  (female) =  $0.9H^{1}-92$ 

(H=height in cm; W=weight in kg)

The weight used for calculation should be obtained prior to study drug administration on Cycle 1 Day 1 (+/- 14 days) and thereafter should only be modified for significant ( $\geq$  10%) changes in body weight (not influenced by weight gain or loss attributed to fluid retention).

Preparation and Administration

Only qualified personnel who are familiar with procedures that minimize undue exposure to them and to the environment should undertake the preparation, handling, and safe disposal of chemotherapeutic and investigational agents. Mirvetuximab soravtansine will be administered at the investigational site. Investigational product should be prepared and dispensed by an appropriately qualified and experienced member of the study staff (eg, physician, nurse, physician's assistant, practitioner, or pharmacist) as allowed by local, state, and institutional guidance

The desired amount should be withdrawn from the vial(s) and diluted using 5% dextrose or 5% D-glucose to a final concentration as outlined in Section 8.1.7. Note: Mirvetuximab soravtansine is incompatible with saline (0.9% sodium chloride). Therefore, dilutions must be made using 5% dextrose or 5% D-glucose. Infusion bags must be labeled with the protocol number, patient number, storage temperature, dose, and volume of mirvetuximab soravtansine filtered into the bag, or according to institutional protocol. Light protection is not required for prepared IMGN853. The infusion must be completed within 8 hours of preparation.

If necessary, study drug from different drug lots may be mixed in a single-dose administration.

Mirvetuximab soravtansine should be administered at a rate of 1 mg/min; after 30 minutes, the rate can be increased to 3 mg/min if well tolerated. If well tolerated after 30 minutes at 3 mg/min, the mirvetuximab soravtansine infusion rate may be increased to 5mg/min. Subsequent infusions may be delivered at the tolerated rate. For patients who have been administered mirvetuximab soravtansine as a prior anti-cancer therapy, mirvetuximab soravtansine should be administered at the tolerated rate of prior mirvetuximab soravtansine infusions. Therefore, the overall length of infusion will vary depending on dose and patient tolerability. Following

infusion, the IV line should be flushed with 5% dextrose or 5% D-glucose as needed to ensure delivery of the full dose.

In combination, mirvetuximab soravtansine should be administered first, followed by pembrolizumab. Mirvetuximab soravtansine will be administered as an IV infusion following preparation as outlined in Section 8.1.7.

#### Drug, Tubing and Filtration

An IV tubing administration set with a 0.2 micron or 0.22 micron in-line filter must be used for infusion. Refer to section 8.1.4 for more information.

#### **Observation Period**

Patients will be carefully observed during each infusion and vital signs taken as outlined in the Study Calendar. They will remain in the clinic under observation for 2 hours after the completion of the first infusion of mirvetuximab soravtansine, and for at least 1 hour after each subsequent infusion, during which pembrolizumab infusion can be administered. The observation period will start after completion of the mirvetuximab soravtansine infusion for all infusions.

#### Infusion Reactions

Some patients treated with IV infusions of therapeutic drugs have experienced concurrent infusion-related reactions (see CTCAE Version 5.0). The signs and symptoms may vary and include for example, headache, fever, facial flushing, pruritus, myalgia, nausea, chest tightness, dyspnea, vomiting, erythema, abdominal discomfort, diaphoresis, shivers, lightheadedness, hypotension, palpitations, and somnolence. Anaphylaxis might occur at any time during an infusion. Before any infusion is started, appropriate medical personnel, medication (e.g. epinephrine, inhaled beta agonists, antihistamines, and corticosteroids), and other required resources to treat anaphylaxis must be readily available. In general, Investigators should manage acute allergic or hypersensitivity reactions according to institutional practices. General guidelines for the management of acute infusion-related reactions and for subsequent retreatment are provided in Table 1. Delayed infusion-related reactions may occur; therefore, patients should be advised to seek immediate medical treatment if symptoms newly develop and/or recur after discharge from clinic.

### Table 1: Management Guidelines for Potential Mirvetuximab Soravtansine Infusionrelated Reactions

CTCAE v5.0 Severity Grade	Management	
Grade 1 Mild reaction; infusion interruption not indicated; intervention not indicated Grade 2 Therapy or infusion interruption indicated but responds promptly to symptomatic treatment (e.g., antihistamines, NSAIDs, narcotics, IV fluids); prophylactic medications indicated for ≤24 hrs	
 
Maintain infusion rate unless progression of symptoms to ≥ Grade 2; if symptoms worsen, refer to guidelines below
 
Promethazine (or equivalent) 150 mg PO per day for nausea (or equivalent)
 
Diphenhydramine (or equivalent) 25-50 mg PO or IV prn
 
Methylprednisolone 125 mg (or equivalent) IV prn
 
Interrupt infusion and disconnect infusion tubing from patient
 
Promethazine (or equivalent) 150 mg PO per day for nausea
 
Diphenhydramine (or equivalent) 150 mg PO per day for nausea
 
Diphenhydramine (or equivalent) 25-50 mg PO or IV prn
 
Acetaminophen (or equivalent) 25-50 mg PO or IV prn
 
Acetaminophen (or equivalent) 650 mg PO prn
 
Methylprednisolone 125 mg (or equivalent) IV prn
 
After recovery from symptoms, resume the infusion at 50% of the previous rate and if no further symptoms appear, gradually increase rate until infusion is completed.
 
For subsequent dosing in future cycles, patients should be pre-medicated with dexamethasone (or equivalent) 8 mg PO BID the day prior to drug administration and acetaminophen (or equivalent) 650 mg PO and diphenhydramine (or equivalent) 25-50 mg PO 30-60 minutes prior to dosing.
 
	
Grades 3 or 4 Grade 3: Prolonged (i.e. not rapidly responsive to symptomatic medication and/or brief interruption of infusion); recurrence of symptoms following initial improvement; hospitalization indicated for clinical sequelae OR Grade 4: Life-threatening consequences, urgent intervention indicated	
 
Immediately stop infusion and disconnect infusion tubing from subject
 
Administer diphenhydramine (25-50 mg) IV (or equivalent)
 
Administer IV steroids (methylprednisolone (or equivalent) up to 0.5mg/kg Q 6h) to treat ongoing reaction and prevent recurrence
 
Administer bronchodilators (nebulized albuterol/salbutamol, 2.5-5 mg in 3 mL of saline or equivalent) as medically indicated
 
Administer normal saline as medically indicated
 
Administer epinephrine (0.2-0.5 mL of a 1:1000 dilution (0.2-0.5 mg) SQ or IM) as medically indicated. Epinephrine should only be used if all other treatment methods fail to manage the infusion-related reaction.
 
Advise patient to seek emergency treatment and notify investigator/clinic if the infusion-related symptoms recur after discharge from clinic.
 
Report as a serious adverse event (see Section 7)
 
Permanently discontinue study medication treatment
 
	

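### Table 1 makes epinephrine a last resort in severe mirvetuximab infusion reactions, with no exception for anaphylaxis, while Table 2 calls for it at once

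*Combined protocol and SAP*

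**What the plan says.** Section 5.3.1, under Infusion Reactions, covers mirvetuximab. It warns: "Anaphylaxis might occur at any time during an infusion". It requires personnel, epinephrine and other resources for treating anaphylaxis to be on hand before any infusion starts. It continues: "In general, Investigators should manage acute allergic or hypersensitivity reactions according to institutional practices". The next sentence refers the reader to Table 1 for general guidelines on acute infusion-related reactions.

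Table 1 has one row for Grades 3 and 4 together. Its upper end is defined as "Grade 4: Life-threatening consequences, urgent intervention indicated". After stopping the infusion, the row lists an IV antihistamine, IV steroids, bronchodilators, saline and then epinephrine. The epinephrine entry closes with: "Epinephrine should only be used if all other treatment methods fail to manage the infusion-related reaction". No line of Table 1 mentions anaphylaxis.

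Section 5.3.2 covers pembrolizumab. Its Infusion Reactions text counts anaphylaxis among the severe reactions. In the Grades 3 or 4 row of Table 2, epinephrine carries a footnote directing its immediate use in anaphylaxis. The spelling of that footnote is garbled in the extracted text, but its meaning is clear.

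**The concern.** Two emergency tables in one protocol give different priorities for the same drug in the same kind of event. A clinician facing anaphylaxis during mirvetuximab who follows the Grade 3 and 4 row would hold epinephrine until everything else had failed. The same clinician facing anaphylaxis during pembrolizumab would give it at once.

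Both drugs are given on Day 1, mirvetuximab first (Section 5.1). Pembrolizumab may be infused during the observation period after mirvetuximab (Sections 5.3.1 and 8.1.8), and Section 5.3.1 warns of delayed infusion-related reactions. A reaction in that window could plausibly be due to either drug. Staff should not have to decide which one before choosing the treatment. What is at stake is patient safety, not the statistical design.

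**Working it through.** No arithmetic beyond a count applies, so the check is a comparison of the texts.

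**1. Does the Table 1 row reach anaphylaxis?** The row includes life-threatening reactions. The text introducing the table raises anaphylaxis under the heading Infusion Reactions, and its list of infusion-reaction signs includes dyspnea, chest tightness and hypotension. The protocol has no separate mirvetuximab algorithm for anaphylaxis. The natural place for staff to look is therefore the Grade 3 and 4 row.

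**2. What comes before epinephrine in that row?**

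| Order | Treatment | Condition |
|---|---|---|
| 1 | "Administer diphenhydramine (25-50 mg) IV (or equivalent") | none |
| 2 | "Administer IV steroids (methylprednisolone (or equivalent) up to 0.5mg/kg Q 6h") | none |
| 3 | Nebulized bronchodilator | where medically indicated |
| 4 | "Administer normal saline as medically indicated" | as quoted |
| 5 | Epinephrine | where medically indicated, then restricted to failure of all other methods |

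Four drug or fluid treatments precede epinephrine: 2 unconditional + 2 conditional = 4. Read literally, epinephrine waits behind at least the antihistamine and the steroid, and behind the other two where they are indicated.

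**3. How do the two sentences of the epinephrine entry fit together?** The join reads: "SQ or IM) as medically indicated. Epinephrine should only be used if all other treatment methods fail". The first sentence leaves the decision to clinical indication. The second, more specific sentence then narrows it, and anaphylaxis is not exempted.

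**4. How does Table 2 compare?**

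| | Table 1, mirvetuximab | Table 2, pembrolizumab |
|---|---|---|
| Grades covered by the row | 3 and 4 | 3 and 4 |
| Epinephrine in general | only after all other methods fail | one of several options |
| Epinephrine in anaphylaxis | no separate instruction, so the restriction applies | immediately |

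The conflict is confined to anaphylaxis. For other Grade 3 or 4 reactions, Table 2 merely lists epinephrine among the options, which is compatible with Table 1.

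**5. Can the effect be sized?** Table 1 gives no interval between steps, and the documents report no rate of Grade 3 or 4 infusion reactions or anaphylaxis with mirvetuximab. Neither a delay nor an expected number of patients can be derived.

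**The case against.** The strongest reply is that the text introducing Table 1 already sends anaphylaxis elsewhere. It mentions anaphylaxis, requires epinephrine to be at hand for it, says allergic and hypersensitivity reactions generally follow institutional practice, and only then offers Table 1 for infusion-related reactions. On that reading Table 1 needs no exception, because anaphylaxis never falls under it. The table is also labelled as guidance, which leaves room for judgement, and its epinephrine entry begins by deferring to medical indication. Finally, the tables concern different products and Table 1 does not mention anaphylaxis, so this is an omission rather than two opposed statements about anaphylaxis.

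Part of this stands. The institutional-practice reading is possible, and experienced clinicians may well override the restriction, which limits the likely harm. But a general deferral is not a carve-out. It leads straight into Table 1 without saying which prevails, within a section that treats anaphylaxis as an infusion reaction. Having epinephrine available says nothing about when to give it. Calling the table guidance does not change what it advises, and the omission matters because the restriction is worded to cover the whole row.

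**Conclusion.** The point holds. For anaphylaxis during mirvetuximab, Table 1 as written gives a worse emergency instruction than the protocol's own Table 2 gives for pembrolizumab. It should be corrected.

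The conclusion rests on reading the Grade 3 and 4 row as covering anaphylaxis. The row's scope and the introductory text support that reading, though no sentence says so outright. The standard applied is the protocol's own, taken from Table 2. No claim is made about how often the situation will arise, how long treatment would be delayed, or other severe reactions.

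**What to change.** In Table 1, Grades 3 or 4, add a clause to the end of the restriction on epinephrine: except in anaphylaxis, when epinephrine should be given immediately. If the sponsor's medical team prefers, the whole sentence can be replaced by the anaphylaxis instruction from Table 2. Either change gives both tables the same instruction for anaphylaxis.

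The cost is one clause of amendment wording, with no change to the design, sample size or analysis. If the intention was always for institutional practice to govern anaphylaxis, the clause removes the ambiguity at almost no cost.
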